3.3. Objectives and Hypotheses

3.3.1. Primary Hypotheses and Objective

To determine whether the provision of a service that delivers smartphone-assisted PST specifically designed for men who present to the Emergency Department with self-harm, results in fewer suicides and/or contacts with Emergency Departments for self-harm, compared with usual care, in the year after the index episode.

We anticipate that in sites implementing a service that delivers smartphone-assisted PST specifically designed for men, 12 months after the index episode, there will be:

- 1. Fewer deaths by suicide; and/or
- 2. Fewer contacts with the Emergency Departments in Ontario for the repetition of self-harm.

3.3.2. Secondary Hypotheses and Objectives

The key secondary objectives are to determine, compared to usual care, whether the provision of a service that delivers smartphone-assisted PST specifically designed for men who present to the Emergency Department with self-harm, results in:

- 1. Lower suicide rates;
- 2. Fewer contacts with any Emergency Departments in Ontario for the repetition of self-harm;
- 3. Fewer contacts with any Emergency Department in Ontario for any reason;
- 4. Fewer admissions to hospital for any reason;
- 5. Fewer outpatient appointments for any reason at any hospital in Ontario;
- 6. Lower mortality rates, not related to suicide;
- 7. Lower use of primary care services (defined by contact with a family physician); and/or
- 8. Decreased costs to the health care system, including physician, hospitalization, Emergency Department, and other costs.

3.4. Trial Design

This is a pragmatic, multicentre pre- and post-design cluster RCT comparing the offer of a service that delivers smartphone-assisted PST to usual care, in men who present to the Emergency Department with self-harm. We have chosen a cluster randomized design because we are testing the introduction of a service for suicidal men that addresses both the need to manage the transition from the Emergency Department to outpatient care and the provision of care specifically designed for men who have intentionally self-harmed.

By randomizing entire sites with a waiver of informed consent for data collection with inclusion of all eligible men using routinely collected data, external validity of the study is maximized, in comparison to an individually randomized trial with a requirement to seek informed consent (refer to Section 5.3 Consent).

4. METHODS

4.1. Participants, Interventions and Outcomes

4.1.1. Study Setting

This multicenter cluster RCT will be conducted in 25 Emergency Departments in Ontario. The unit of randomization is selected Emergency Departments in each region (refer to Appendix A for a complete list of intervention and control sites).

4.1.2. Eligibility Criteria

Sites were deemed eligible if they averaged at least 50 self-harm presentations by men per year. and an absolute re-presentation rate of at least 6 over three years. This resulted in a list of 25 eligible Emergency Departments in Ontario. Eligible patients will be identified in ICES, using the following criteria:

Incl	usion Criteria
1	Patient has presented with an index episode of intentional self-harm at an eligible
1.	Emergency Department in Ontario, Canada.
2.	Patient is biologically male.
3.	Patient is 18 years of age or older.
4.	Patient has a valid OHIP number.
Exc	lusion Criteria
1	Patient has presented to the Emergency Department for a reason other than intentional
1.	self-harm at an eligible Emergency Department in Ontario, Canada.
2.	Patient is biologically female.
3.	Patient is under 18 years of age.
4.	Patient does not have a valid OHIP number.

Intentional self-harm is defined as intentional self-poisoning or self-injury, whether or not there is evidence that the act was intended to result in death. This will be identified using ICD-10-CM codes T14.91, X71-X83 ICD-10 codes from health administrative databases held at ICES.

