4.1.4. Outcomes

The primary outcome measure will be a composite of the incidence of suicides and/or re-presentations to any Emergency Department in Ontario for self-harm in the year after the index episode of self-harm. The incidence of suicide and re-representation to Emergency Department will be measured using ICD-10-CM codes T360-T50992, T510-T6592, T71112-T71232, X71-X83 (refer to Appendix A for full list of codes and descriptors) [46]. Individuals who died by suicide will be identified in ICES using the Vital Statistics - Death Database. A potential problem with the outcome measures in this trial is that the intervention may also change help-seeking behaviour. That is, men may seek out healthcare that they would not have in the past, which may lead to an increase in re-presentations to the Emergency Department for patients in the intervention group. In order to explore changes to health-related help-seeking, we will also collect data on primary care and hospital outpatient care not driven by emergencies through ICES. This will be measured in ICES, using the Ontario Health Insurance Plan (OHIP) Claims Database and National Ambulatory Care Reporting System Metadata (NACRS). We will also address this through a sub-study of smartphone-assisted PST.

The secondary outcome measures will include total number of suicides; representations to any Emergency Department in Ontario for the repetition of self-harm; representations to any Emergency Department in Ontario for any reason; other health system use including use of primary care and hospital outpatient appointments; mortality not related to suicide; and, health system costs within one year which will inform an economic analysis. All outcomes will be identified and measured using routinely collected data housed at ICES. Men who present with intentional self-harm in the study Emergency Departments will be identified from ICES administrative health data.

	Justification	Data Source	Data Collection Period
Primary Outcome Va	riable (composite outco	ome variable)	
Death by Suicide	To assess the clinical	ORGD, NACRS	Baseline; 12 months
and/or re-	impact of the	(ICES)	
presentation to any	provision of a		
Emergency	smartphone-assisted		
Department in	PST service.		
Ontario for Self-harm			
Secondary Outcomes	Secondary Outcomes		
Death by Suicide	To assess the clinical	ORGD (ICES)	Baseline; 12 months
	impact of the		
	provision of a		
	smartphone-assisted		
	PST service.		

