4.1.5. Sample Size

Power calculations for this trial were carried out within the logistical and practical constraints of the trial; in particular, a maximum of 25 sites are available for randomization, whereas the intervention can be implemented at only 10 sites. Consistent with previous clinical trials, we would consider a minimum relative reduction of 50% in the repetition rate to be both clinically important and achievable [47-49]. To conduct an accurate power calculation, we obtained data from ICES regarding the number of presentations with selfharm by men and the re-presentation rate to every hospital in Ontario from 2012 to 2014. Using these data, we calculated an anticipated baseline repetition rate (primary outcome) after 12 months of 13%. We also calculated an intracluster correlation coefficient (ICC) of 0.01 and an inter-period correlation of 0.008 (to account for over time correlations between pre- and post-intervention measures of the primary outcome). Given an average cluster size of 80 men and a coefficient of variation of cluster sizes (to account for imbalances in sizes) of 30%, 10 intervention clusters and 15 control clusters (2000 men) achieve 90% power to detect the minimum important difference. With 80% power, the detectable difference is a relative reduction of 41%, i.e., from a control arm rate of 13% to an intervention arm rate of 7.7% (an absolute reduction of 5.3%).

> Study Protocol Version 1, Date: December 1, 2017 Page 20 of 51

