4.3. Data Collection, Management and Analysis

4.3.1. Data Collection

Data Collection Methods

Trial outcomes comprise routinely collected data which are housed at ICES. Access to all outcome data has been agreed upon with ICES.

Retention

Emergency Departments

Once randomization of the study sites is completed, the Principal Investigator will contact members of the Department of Psychiatry and Department of Emergency Medicine at each intervention site to be site co-Investigators, to assume responsibility for all study-related activities at their respective site. They will act as study "champions" and, in conjunction with Research Assistants, will provide study support to Emergency Department staff members.

Each study site will also receive training, as described in Section 4.1.3 Interventions, in the identification and management of self-harm as well as access to an electronic booking system for study referrals and Research Assistant(s) to coordinate all study-related activities.

Participants

This study will focus on the evaluation of a complex intervention based on routinely collected population-level health data. Given this, there will be no individual participant

recruitment for this study. All data collected through ICES will thus be included in the primary analysis irrespective of uptake of the smartphone-assisted PST.

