6.2. Appendix B – ICD-10-CM Self-Harm Codes Included in Collection

Code*	Description
Self-Injury	
X710XXA, X710XXD,	Intentional self-harm by drowning or submersion while in
X710XXS	bathtub.
X711XXA, X711XXD,	Intentional self-harm by drowning or submersion while in
X711XXS	swimming pool.
X712XXA, X712XXD,	Intentional self-harm by drowning or submersion after
X712XXS	jump into swimming pool.
Self-Injury	
X713XXA, X713XXD,	Intentional self-harm by drowning and submersion in
X713XXS	natural water.
X718XXA, X718XXD,	Other intentional self-harm by drowning or submersion
X718XXS	Other mentional sen-nami by drowning of submersion.
X719XXA, X719XXD,	Intentional self-harm by drowning or submersion,
X719XXS	unspecified.
X72XXXA, X72XXXD,	Intentional self-harm by handoun discharge
X72XXXS	intentional sent narm by nanogan disenarge.
X730XXA, X730XXD,	Intentional self-harm by shotgun discharge
X730XXS	intentional sent narm by shotgan alsonarge.
X731XXA, X731XXD,	Intentional self-harm by hunting rifle discharge
X731XXS	intentional ben nami og namming mile albenarge.
X732XXA, X732XXD,	Intentional self-harm by machine-gun discharge
X732XXS	intentional ben name by machine gan albenaige.
X738XXA, X738XXD,	Intentional self-harm by other larger firearm discharge
X738XXS	
X739XXA, X739XXD,	Intentional self-harm by unspecified larger firearm
X739XXS	discharge.
X7401XA X7401XD	
X7401XS	Intentional self-harm by airgun.
X7402XA X7402XD	
Λ/402ΛΑ, Λ/402ΛD, V7402VS	Intentional self-harm by paintball gun.
A/402AD	

Self-Injury	
X7409XA, X7409XD,	Intentional self-harm by other gas, air or spring operated
X7409XS	gun.
X748XXA, X748XXD,	Intentional calf harm by other firearm discharge
X748XXS	intentional sen-narm by other meanin discharge.
X749XXA, X749XXD,	Intentional calf harm by unanacified firearm discharge
X749XXS	intentional sen-narm by unspecified meanin discharge.
X75XXXA, X75XXXD,	Intentional salf harm by avalagive material
X75XXXS	intentional sen-narm by explosive material.
X76XXXA, X76XXXD,	Intentional salf harm by smales, fire and flamos
X76XXXS	intentional sen-nami by smoke, me and mames.
X770XXA, X770XXD,	Intentional self harm by steam or bot vanours
X770XXS	intentional sen-narm by steam of not vapours.
X771XXA, X771XXD,	Intentional self-harm by hot tan water
X771XXS	intentional sem-narm by not tap water.
X772XXA, X772XXD,	Intentional self-harm by other hot fluids
X772XXS	intentional ben nami by other not nards.

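### The codes that admit men to the cohort (T14.91, X71-X83) omit the poisoning codes, contradicting the protocol's own self-harm definition and its outcome code list

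*Protocol*

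**What the plan says.** Section 4.1.2 gives the concept first: "Intentional self-harm is defined as intentional self-poisoning or self-injury", irrespective of intent to die. The next sentence gives the working rule: "This will be identified using ICD-10-CM codes T14.91, X71-X83 ICD-10 codes from health administrative databases held at ICES". It does not refer to an appendix.

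Section 4.1.4 says suicide and re-presentation will be "measured using ICD-10-CM codes T360-T50992, T510-T6592, T71112-T71232, X71-X83", and tells the reader to "refer to Appendix A for full list of codes and descriptors". Section 4.1.1 describes Appendix A as the site list. The codes are in section 6.2, Appendix B, titled "ICD-10-CM Self-Harm Codes Included in Collection".

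There is no individual recruitment. Section 4.3.1 says "All data collected through ICES will thus be included in the primary analysis". For planning, section 4.1.5 reports that "we obtained data from ICES regarding the number of presentations with selfharm by men", and derives from those data a 13% repetition rate and the two correlations used. It does not name the codes behind the counts. Section 4.1.2 likewise says "Sites were deemed eligible if they averaged at least 50 self-harm presentations by men per year" without naming codes.

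**The concern.** The entry rule and the outcome rule describe different events, and the entry rule does not match the definition beside it. In a trial built wholly from administrative records the code string does the work of recruitment: with the age, sex and OHIP conditions, it fixes who is analysed, in both arms and both periods. If an analyst runs section 4.1.2 as printed, men who present with an overdose, the commonest form of self-harm in emergency departments according to section 3.1.1, mostly drop out of the index cohort. The result would then describe mainly men who injure themselves, and would not answer the question in section 3.3.1 about men presenting with self-harm. If the planning counts covered all methods, the stated power would go too.

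**Working it through.** **Comparing the code lists**

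| Code block | Heading in Appendix B | Index (4.1.2) | Outcome (4.1.4) |
|---|---|---|---|
| X71-X83 | Self-injury | yes | yes |
| T36-T50 | Poisoning | no | yes |
| T51-T65 | Toxic effects | no | yes |
| T71 (includes hanging) | Asphyxiation | no | yes |
| T14.91 | not listed | yes | no |

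Only the injury block is common to both rules. T14.91 can start follow-up but can never count as a repeat, and the protocol does not say what it covers.

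**How many men are affected**

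Section 3.1.1 puts ingestion of an excess of a medicinal or toxic substance at about 80% of episodes and injury at 15-20%, both sexes together. Applied directly, 15-20% of 80 is 12-16 men per site, or 300-400 in all. The split in men and the reach of T14.91 are not given, so I take a loss of 60-85% as an assumption: 80 × 0.15 = 12 to 80 × 0.40 = 32 men per site, or 300-800 of 25 × 80 = 2,000.

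**Power**

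Inputs from section 4.1.5: ICC 0.01, inter-period correlation 0.008, coefficient of variation 0.30, 10 intervention and 15 control sites, 13% control rate, 50% relative reduction (6.5%). Two-sided 5% and a normal approximation are my assumptions. With m men per site:

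- V = p1(1−p1)/(10m) + p0(1−p0)/(15m)
- design effect DE = 1 + ((1 + CV²)m − 1) × ICC
- r = 0.008m / (1 + (m − 1) × 0.01)
- variance = V × DE × (1 − r²) if baseline-adjusted, or V × DE × 2(1 − r) for a change contrast
- power = Φ((p0 − p1)/SE − 1.96)

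The plan's own case, m = 80: V = 0.000170, DE = 1 + (87.2 − 1) × 0.01 = 1.862, r = 0.64/1.79 = 0.358. The change contrast has SE 0.0202, so 0.065/0.0202 = 3.22 and power is 90%, the stated figure. The baseline-adjusted form has SE 0.0166 and power 97%.

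| Men per site | DE | r | Baseline-adjusted | Change contrast |
|---|---|---|---|---|
| 12 | 1.121 | 0.086 | 45% | 27% |
| 16 | 1.164 | 0.111 | 55% | 34% |
| 24 | 1.252 | 0.156 | 69% | 47% |
| 32 | 1.339 | 0.195 | 79% | 57% |
| 80 | 1.862 | 0.358 | 97% | 90% |

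An injury-only group may have another repetition rate. With a control rate of 10% (assumed) to 19.3% (the figure for men elsewhere in section 3.1.1), 12-32 men per site give 35-94% baseline-adjusted or 21-77% for the change contrast.

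**Did the planning counts include poisonings?**

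Suppose the 2,000 men came from injury codes alone. With injury at 15-20% of episodes, these 25 sites would see 2,000/0.20 = 10,000 to 2,000/0.15 = 13,333 men for all methods. Section 3.1.1 gives 8,250 presentations a year in the whole province and four in ten being men: 8,250 × 0.4 = 3,300. Its higher estimate gives 16,000 × 0.4 = 6,400. Injury would have to be at least 2,000/6,400 = 31% of men's episodes to fit. Taking 80 as a one-year count and four in ten as the male share in Ontario, the planning counts very probably covered poisonings.

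**The case against.** The strongest reply is that this is a slip in one sentence. The definition stands right beside the code string, and Appendix B is titled as the codes to be collected. If the planning extraction already covered poisonings, the team evidently has a broader list in use, so the chance that the cohort is really built from injury codes alone is modest. That is fair as a reading of intent. But section 4.1.2 is the only working rule for cohort entry, it does not cite Appendix B, and T14.91 shows that the string is not simply a shortened outcome list. A programmer could follow it in good faith.

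A second reply is that T14.91 might bring some poisonings and hangings back, and that the power range rests on several assumptions. Both points stand. The reach of T14.91 is unknown, and the power figures are illustrations conditional on a literal run and on all-method planning counts. The contradiction between the lists does not depend on them.

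Two further points are sound but separate. Appendix B codes carry suffixes for initial encounter, subsequent encounter and sequela, and section 4.1.2 mentions both ICD-10-CM and ICD-10. Both already affect the existing X71-X83 string, and both are worth settling when the list is revised.

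**Conclusion.** The concern holds and must be fixed before data are extracted. The stated entry rule contradicts the definition next to it and differs from the outcome rule in both directions: three blocks count only as outcomes, and one code counts only as an index event. Followed as written, it gives a mainly injury-only cohort.

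The size is conditional. If the planning counts covered all methods and 60-85% of men are lost, power at a 13% control rate falls from the stated 90% to 27-57% on the contrast that reproduces that 90%, or to 45-79% if baseline-adjusted. This holds the ICC, the inter-period correlation and the variation in cluster size at their planning values. Whatever the power, the estimate would apply to a different population from the one the trial sets out to study.

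**What to change.** Use one code list for index and outcome:

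- In 4.1.2, replace the string with the Appendix B intentional self-harm codes: T36-T50, T51-T65, T71 and X71-X83.
- In 4.1.4, cite the same list and correct the pointer from Appendix A to Appendix B.
- For T14.91, either justify it and add it to 4.1.2, 4.1.4 and Appendix B, or drop it.
- In 4.1.5, state which codes produced the ICES counts behind the 80 men per site and the 13% rate, and restate the power if they differ from the final list.

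The cost is text edits in two sections, one sentence in 4.1.5, and one appendix row only if T14.91 stays. No new data collection is needed. A re-count at ICES is required only if the planning counts used another list.

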4.1.3. Interventions

Emergency Departments randomized to the study intervention will receive:

- 1. Staff education incorporated into regular teaching rounds at least twice a year about the management of self-harm in the Emergency Department. This will include the dissemination of guidelines (APA, NICE, SPRC and CCSMH) [45] on how to ask questions about suicide, assessment of suicide risk, the creation of a management plan and how to refer patients to local mental health resources, including the study.
- 2. Written materials developed by service users to be given to men who self-harm that outline local resources, distress centre helplines and follow-up arrangements. The materials will be available in French and English and we will be discussing with Aboriginal partners translation of some materials into Ojibwe or Oji Cree.
- 3. The option to refer men who self-harm to a service that will deliver smartphoneassisted PST specifically designed for men.

Emergency Departments randomized to the control group will continue to provide treatment using established pathways. This typically constitutes assessment of clinical risk, the need for medical intervention to treat the effects of self-harm, and for inpatient or outpatient mental healthcare. All men who present to the Emergency Department with intentional self-harm will have access to the full range of mental health and other services that are usually available to individuals in the different regions. This includes inpatient admission and other crisis services.

4.1.4. Outcomes

The primary outcome measure will be a composite of the incidence of suicides and/or re-presentations to any Emergency Department in Ontario for self-harm in the year after the index episode of self-harm. The incidence of suicide and re-representation to Emergency Department will be measured using ICD-10-CM codes T360-T50992, T510-T6592, T71112-T71232, X71-X83 (refer to Appendix A for full list of codes and descriptors) [46]. Individuals who died by suicide will be identified in ICES using the Vital Statistics - Death Database. A potential problem with the outcome measures in this trial is that the intervention may also change help-seeking behaviour. That is, men may seek out healthcare that they would not have in the past, which may lead to an increase in re-presentations to the Emergency Department for patients in the intervention group. In order to explore changes to health-related help-seeking, we will also collect data on primary care and hospital outpatient care not driven by emergencies through ICES. This will be measured in ICES, using the Ontario Health Insurance Plan (OHIP) Claims Database and National Ambulatory Care Reporting System Metadata (NACRS). We will also address this through a sub-study of smartphone-assisted PST.

The secondary outcome measures will include total number of suicides; representations to any Emergency Department in Ontario for the repetition of self-harm; representations to any Emergency Department in Ontario for any reason; other health system use including use of primary care and hospital outpatient appointments; mortality not related to suicide; and, health system costs within one year which will inform an economic analysis. All outcomes will be identified and measured using routinely collected data housed at ICES. Men who present with intentional self-harm in the study Emergency Departments will be identified from ICES administrative health data.

	Justification	Data Source	Data Collection Period
Primary Outcome Va	riable (composite outco	ome variable)	
Death by Suicide	To assess the clinical	ORGD, NACRS	Baseline; 12 months
and/or re-	impact of the	(ICES)	
presentation to any	provision of a		
Emergency	smartphone-assisted		
Department in	PST service.		
Ontario for Self-harm			
Secondary Outcomes	Secondary Outcomes		
Death by Suicide	To assess the clinical	ORGD (ICES)	Baseline; 12 months
	impact of the		
	provision of a		
	smartphone-assisted		
	PST service.		
Re-presentation to	To assess the clinical	NACRS (ICES)	Baseline; 12 months
any Emergency	impact of the		
Department in	provision of a		
Ontario for Self-harm	smartphone-assisted		

Table 2. Outcome Measures

	PST service.		
Re-presentation to any Emergency Department for any reason	To assess the clinical impact of the provision of a smartphone-assisted PST service.	NACRS (ICES)	Baseline; 12 months
Admission to any hospital in Ontario for any reason	To assess the clinical impact of the provision of a smartphone-assisted PST service.	NACRS (ICES)	Baseline; 12 months
Hospital outpatient appointments in Ontario for any reason	To assess the clinical impact of the provision of a smartphone-assisted PST service.	OHIP (ICES)	Baseline; 12 months
Primary care appointments	To assess the clinical impact of the provision of a smartphone-assisted PST service.	OHIP (ICES)	Baseline; 12 months
Mortality for reasons other than suicide	To assess the clinical impact of the provision of a smartphone-assisted PST service.	ORGD (ICES)	Baseline; 12 months
Total Health Care Costs	To assess the economic impact of the provision of a smartphone-assisted PST service.	OHIP, DAD, NACRS, NRS, CCRS, OMHRS, ODB, ADP (ICES)	Baseline; 12 months
Physician Health Care Costs	To assess the economic impact of the provision of a smartphone-assisted PST service.	OHIP (ICES)	Baseline; 12 months
Emergency Department Health Care Costs	To assess the economic impact of the provision of a smartphone-assisted PST service.	NACRS (ICES)	Baseline; 12 months
Hospitalization Health Care Costs	To assess the economic impact of the provision of a smartphone-assisted PST service.	DAD (ICES)	Baseline; 12 months
Other Health Care Costs	To assess the economic impact of the provision of a	NRS, CCRS, OMHRS, ODB, ADP (ICES)	Baseline; 12 months

	smartphone-assisted		
	PST service.		
Prognostic outcome n	neasures		
Age	To assess differences	RPDB (ICES)	Baseline
	between subgroups.		
Previous	To assess differences	NACRS (ICES)	Baseline
hospitalization for	between subgroups.		
self-harm			
Previous	To assess differences	NACRS (ICES)*	Baseline
hospitalization for	between subgroups.		
substance use			

* Appendix B for list of ICD-10-CM codes.

Data Sources: ADP, Assistive Devices Program; CCRS, Continuing Care Reporting System; DAD, Discharge Abstract Database; NACRS, National Ambulatory Care Reporting System; NRS, National Rehabilitation Reporting System; ODB, Ontario Drug Benefit Claims; OHIP, Ontario Health Insurance Plan Claims Database; OMHRS, Ontario Mental Health Reporting System; RPBD, Registered Persons Database; ORGD, Vital Statistics – Death.

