Self-harm has a strong association with suicide: 1.6% of people presenting to Emergency Departments with self-harm will die by suicide within one year (95% confidence interval 1.2 to 2.1%), with the incidence rate being almost double in men compared to women (2.7% vs 1.2%) [8]. Approximately four percent of individuals who have presented to the Emergency Department for the treatment of self-harm die by suicide within five years of their index presentation [8]. This risk is more than 50 times greater than the general population rate and is associated with a 40-year reduction in average life expectancy [8]. A recent population-based cohort study investigating administrative datasets in the province of Ontario discovered that: "all-cause mortality following a first episode of self-poisoning was 1,107 per 100,000 person-years...[with] nearly half of all deaths being suicides, accidents or [of] undetermined intent"[9].

Presentation to the Emergency Department with self-harm is a major identifiable risk factor for suicide, with at least one quarter of deaths by suicide being preceded by a hospital visit due to non-fatal self-harm in the previous year [10-11]. As such, it is likely that any reduction in the repetition of self-harm will be mirrored by a decline in subsequent deaths by suicide. The Canadian Association for Suicide Prevention (CASP) blueprint for a national suicide prevention strategy has also identified people who have attended hospital because of non-fatal self-harm as a high risk group to target in order to prevent suicide [12]. Mortality from non-suicidal causes is also high for those who self-harm, with significantly more than the expected numbers of deaths from natural causes and from accidents [13]. These premature deaths are greatly over-represented among young people and the potential years of life lost in the community are many.

Individuals who self-harm are frequent users of health and social services [14]. Approximately 10% of those who present in an Emergency Department following self-harm will engage in repeat self-harm in the following month and up to 27% after six months [15]. Recurrent self-harm is associated with significant distress and many unresolved interpersonal problems [16].

Why Focus on Men?

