T65812A, T65812D, T65812SToxic effect of latex, intentional self-harm.T65822A, T65822D, T65822SToxic effect of harmful algae and algae toxins, intentional self-harm.T65832A, T65832D, T65832SToxic effect of fiberglass, intentional self-harm.	T656X2A, T656X2D, T656X2S	Toxic effect of paints and dyes, not elsewhere classified, intentional self-harm.
T65822A, T65822D, T65822SToxic effect of harmful algae and algae toxins, intentional self- harm.T65832A, T65832D, T65832SToxic effect of fiberglass, intentional self-harm.	T65812A, T65812D, T65812S	Toxic effect of latex, intentional self-harm.
T65832A, T65832D, T65832SToxic effect of fiberglass, intentional self-harm.	T65822A, T65822D, T65822S	Toxic effect of harmful algae and algae toxins, intentional self- harm.
	T65832A, T65832D, T65832S	Toxic effect of fiberglass, intentional self-harm.

Toxic Effects	
T65892A, T65892D, T65892S	Toxic effect of other specified substances, intentional self-harm.
T6592XA, T6592XD, T6592XS	Toxic effect of unspecified substance, intentional self-harm.

Asphyxiation:	
T71112A, T71112D, T71112S	Asphyxiation due to smothering under pillow, intentional self-
	harm.
T71122A, T71122D, T71122S	Asphyxiation due to plastic bag, intentional self-harm.
T71132A, T71132D, T71132S	Asphyxiation due to being trapped in bed linens, intentional
	self-harm.
T71152A, T71152D, T71152S	Asphyxiation due to smothering in furniture, intentional self-
	harm.
T71162A, T71162D, T71162S	Asphyxiation due to hanging, intentional self-harm.
T71192A, T71192D, T71192S	Asphyxiation due to mechanical threat to breathing due to other
	causes, intentional self-harm.
T71222A, T71222D, T71222S	Asphyxiation due to being trapped in a car trunk, intentional
	self-harm.
T71232A, T71232D, T71232S	Asphyxiation due to being trapped in a (discarded) refrigerator,
	intentional self-harm.

* Note: Please note that all codes end in either A, D or S. These codes refer to (A) Initial Encounter, (D) Subsequent Encounter, or (S) Sequela.

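### The only code set given for suicide is an encounter-based ICD-10-CM list, while suicides come from a death register whose coding is not stated, so suicide ascertainment is badly fixed and may be incomplete or misclassified

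*Protocol*

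**What the plan says.** Section 4.1.4 gives a single measurement rule for the two components of the primary outcome: "The incidence of suicide and re-representation to Emergency Department will be measured using ICD-10-CM codes T360-T50992, T510-T6592, T71112-T71232, X71-X83". It sends the reader to Appendix A for the full list. The list is in fact in section 6.2, "Appendix B – ICD-10-CM Self-Harm Codes Included in Collection".

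The note under that list says of its entries: "Please note that all codes end in either A, D or S". It then explains the endings: "These codes refer to (A) Initial Encounter, (D) Subsequent Encounter, or (S) Sequela".

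The source for deaths is named in the same paragraph of 4.1.4: "Individuals who died by suicide will be identified in ICES using the Vital Statistics - Death Database". Table 2 gives ORGD as the only source for death by suicide and for mortality from other causes, and NACRS for re-presentation with self-harm. The key to the table expands the acronym and no more: "ORGD, Vital Statistics – Death". No section gives a code set for causes of death or says how the register codes them.

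Section 4.1.2, on the index episode, names the classification in two ways in one sentence: "This will be identified using ICD-10-CM codes T14.91, X71-X83 ICD-10 codes from health administrative databases held at ICES".

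**The concern.** A suffix meaning initial encounter, subsequent encounter or sequela describes a contact with care. A death registration is not such a contact. The protocol therefore applies to the death register a list built for visits, and gives no other rule for deciding which deaths are suicides.

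Three outcomes depend on that rule: the primary composite, suicide as a secondary outcome, and mortality for reasons other than suicide. The last comes from the same register, so a suicide that the rule misses can be counted there. The registration data set at the front of the protocol also sets undetermined deaths apart from that outcome, and no code is given for those either.

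Two competent analysts who follow 4.1.4 could report different suicide counts. If the death codes are chosen after the data are cut, part of the primary endpoint will have been defined post hoc.

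**Working it through.** The protocol states no figure for suicide ascertainment, so the main check is to apply the stated rule to the stated source. The arithmetic then shows how many deaths depend on it.

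**1. Three ways to apply the rule to the death register**

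- *Exact match on Appendix B.* Each listed string carries A, D or S. A match needs a cause-of-death field holding an encounter character. The protocol does not say that the register has one.
- *Match on X71-X83 without suffix.* No encounter character is needed. As listed in Appendix B, these codes cover drowning, firearms, explosives, fire, heat, sharp and blunt objects, jumping, vehicle and aircraft crashes, electrocution, cold and other specified means. None is for poisoning or hanging.
- *Match on the T ranges without suffix.* Poisoning and toxic effects are listed only under T36-T65, and hanging only as T71162A/D/S. Intent sits inside the full string: T360X2A is listed as penicillin poisoning with intentional self-harm, and each T entry has a 2 just before its ending (T360X2A, T3692XA, T71162A). The ranges in 4.1.4 start at T360 and T510, which lack that character. Read as an interval, or cut back to a category, they no longer separate self-harm from other poisoning.

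The first two readings can miss suicides. The third can admit deaths that are not suicides.

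**2. Deaths at stake**

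Inputs: 2,000 men, 1,200 control (15 × 80) and 800 intervention (10 × 80), from 4.1.5; one-year suicide risk of 2.7% in men and 1.6% overall, from 3.1.1; 0.5% as an assumed low value.

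- 2,000 × 0.027 = 54 (control 1,200 × 0.027 = 32.4; intervention 800 × 0.027 = 21.6, with no effect)
- 2,000 × 0.016 = 32
- 2,000 × 0.005 = 10

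The low value has some support in 3.1.1, which gives an Ontario all-cause mortality of 1,107 per 100,000 person-years after first self-poisoning, nearly half of it suicide, accident or undetermined. Half of 1.107% is 0.55%, or about 11 deaths in 2,000 for the three together. That figure is not restricted to men and covers first self-poisoning only.

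The 13% baseline in 4.1.5 corresponds to 2,000 × 0.13 = 260 events. If it contains no suicides and the components do not overlap, suicides make up 2.7/15.7 = 17%, 1.6/14.6 = 11% or 0.5/13.5 = 4% of composite events.

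**3. Power**

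Design effect: 1 + ((1 + 0.30²) × 80 − 1) × 0.01 = 1.862. With post-intervention data only and a two-sided 5% test (assumed, as alpha is not stated), 13% against 7.7% gives 79.2%, close to the stated 80%. The same method gives 94.0% for 13% against 6.5%, where the protocol states 90%. None of the variants tried gives both stated figures.

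- If the 13% contains no suicides, as its derivation from re-presentation data suggests, losing them leaves the stated power unchanged.
- If, as an extreme, 2.7 points of the 13% were suicide only and all were lost, the baseline would be 10.3%. Power would fall from 94.0% to 86.8% for a 50% reduction and from 79.2% to 68.5% for a 41% reduction.

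**The case against.** The strongest reply is that the protocol already splits its sources. Section 4.1.4 says that suicides are found through the death database, and Table 2 assigns ORGD to deaths and NACRS to visits. The ranges in 4.1.4 carry no suffix, so nothing there requires a match on the suffixed strings. On this reading only the register's code range is missing, which is a clarification.

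Part of this stands. The sources are separate, and exact matching is not prescribed in so many words. But naming a database does not say which of its deaths count as suicide, and the one rule given for that is the shared list. Reading it without suffixes does not repair it, as step 1 of the working shows. An analyst could strip only the last character and keep the intent marker, but that rule is not written. It also presumes that the register holds ICD-10-CM codes at that level of detail, which the protocol does not say.

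A reader might go further and infer that the rule, run literally, would find few or no suicides and leave the composite as Emergency Department re-presentation alone. The documents do not support that. It would require knowing how the register codes cause of death and assuming an exact match on the suffixed strings. The mixed wording in 4.1.2 does not settle it, since that sentence concerns the index episode and not deaths.

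**Conclusion.** The point holds as a defect in a stated rule: a visit-based list is prescribed for deaths, and no code set suited to the death register is given. Suicide ascertainment can be incomplete or misclassified. The amount is not fixed by the documents and could lie anywhere from negligible to most of the deaths, according to how the register is coded and how the list is matched.

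The scale runs from about 10 suicides in 2,000 men (assumed 0.5%) to about 54 (2.7%), with about 32 at 1.6%. The higher figures take the cited risks as applicable to this population. The share of composite events, 4% to 17%, also assumes that the 13% baseline excludes suicides and that the components do not overlap. Section 4.1.5 labels the 13% both a repetition rate and the primary outcome, so that assumption is open.

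The main harm is to the validity of the composite, the suicide outcome and the non-suicide mortality outcome. The power statement need not change.

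**What to change.** In 4.1.4, give the two components separate rules.

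- **Suicide:** a death within one year of the index episode whose registered cause is intentional self-harm, in the classification that the death register itself uses. Confirm the code range with ICES and list it in the protocol before data are cut.
- **Use of that range:** apply it to the composite and to the suicide outcome, and use its complement for non-suicide mortality. State how undetermined deaths are identified, since the registration data set sets them apart.
- **Emergency Department visits:** restrict Appendix B to these, and confirm with ICES that it is written in the classification of the visit records.
- **Cross-reference:** change the pointer in 4.1.4 from Appendix A to Appendix B.

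The cost is a wording change and a short request to ICES. Design, sample size and data sources stay as they are.
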